Objectives:	 Determine whether providing training and HIVST to select fishermen to distribute to other men in their close social networks increases men's HIV testing uptake; Determine whether network-central promoters and small incentives can improve ART and PrEP uptake among men in their close social networks; and Test the impact of interventions on ART or PrEP retention and adherence. 			
Approach:	In Aim 1, following the study pilot, community selection, and preparation (see 'recruitment and retention plan') the study team will conduct a census/BMU registry verification in study communities to identify the population of men eligible for the study. We will screen, recruit and enroll eligible men who give their informed consent to participate, then measure their close social networks identify network-central, highly-connected men ("promoters") and randomize their close social network (a cluster) to 1:1 intervention and control groups. We will then			

	conduct a baseline survey to collect sociodemographic and baseline sexual behavior data among men in the close social networks. Following this baseline data collection, all promoters will be provided a training. Promoters in the intervention group will receive HIVST training, multiple HIVST for distribution to other men, and a small amount of remuneration. Promoters in the control group will receive basic HIV ducation and training about the study, and will be given vouchers that can be exchanged for HIV tests (standard or free HIVST kits) at nearby health facilities. Using follow-up survey data, we will test the hypothesis that a higher rate of HIV testing will be observed after 3 months among men in networks that receive the intervention compared to control.
Description of Study Intervention:	periods corresponding to the timing of quantitative outcome measurements in Aims 1 through 3. Intervention type: Behavioral intervention trial The intervention strategy is to recruit and train highly socially-connected men to distribute HIVST and provide linkage support (encouragement, along with small
intervention:	distribute mixs) and provide linkage support (encouragement, along with small

Study Duration Participant Duration:	5 Years Approximately 30 months

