8.4 BASELINE SURVEY

Visit 2 for up to n=1000 individuals mapped in the social networks

Based on men who have agreed to be in the study and were mapped to social networks, and the close social network cluster randomized, we will conduct a baseline survey with all network members and their central promoters. This baseline survey will include socio-demographic, health and sexual behaviors, including HIV testing history and will serve as the baseline for a number of measures prior to the study implementation.

The baseline survey is included as an attachment to this protocol.

8.5 **PROMOTER TRAININGS**

Visit 3 for up to n=140 promoters from the study population of up to n=1000 men

All men who are enrolled/consent as promoters (i.e. in both study groups) will participate in mandatory core training sessions. For the intervention group, an enhanced training of up to two days will be facilitated by study personnel and trainers, and will orient them to the study, their role, as well as equip them with enhanced knowledge about HIVST, information about HIV, PrEP, and treatment, including learning about the benefits of HIV testing (materials are included as attachments to this protocol). Promoters will be trained in the usage of oral fluid-based HIV tests (Oraquick Advance, approved for use in Kenya and other countries), and in how to interpret the results of self-tests. Building on prior work of the investigative team, the study team will utilize instruction sheets (with pictures and local language text) that have been developed in the setting (Kenya) to explain self-test usage. The team will also train promoters on how to use motivational interviewing techniques to motivate others to use self-tests, and the importance of confidentiality as a part of the study. For the control group, a basic training will be provided to present the study, importance and benefit of HIV testing, care, and prevention. The training will also cover issues related to confidentiality.

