After the training, the intervention promoters will receive multiple HIV self-test kits for distribution to other men in their close social networks. The HIVST distribution will be as follows: each network-central promoter will receive a test kit for himself, and an addition number of kits (up to 8), for as many of his close network members as identified during the mapping exercise. They also will be given, and asked to distribute to men in their close social networks, transport vouchers for ART or PrEP after HIV self-testing. The voucher worth Ksh 500 (~\$5) will be used for reimbursement when seeking confirmatory testing for HIV and screening for ART or PrEP within 3 months of self-testing at home. The amount reflects prevailing transport and opportunity costs of time. In the session for promoters in the control group, the promoters will be given vouchers with information on facilities with free HIV testing and free self-tests at nearby health facilities, to distribute to men in their close social networks. The control promoters will receive a voucher with information about where to get an HIVST or standard HIV testing within the facilities in the community. The voucher will not have any monetary value. All promoters, in both groups, will be given up to Ksh 1000 (~\$10) for their participation in a full day of training.

Training curriculum is attached to this protocol.

8.6 3-MONTH FOLLOW UP SURVEYS/BASELINE FOR NEW PARTICIPANTS

Up to n=1500 participants

Visit 1 for new participants (those not mapped in the baseline but received self-tests with incentive vouchers (intervention) or referral vouchers (control) from promoters

Visit 3 for baseline mapped and surveyed participants who received self-tests with incentive vouchers (intervention) or referral vouchers (control) from promoters

Visit 4 for promoters who will have participated in the social network survey, baseline survey, and promoter trainings (visits 1 2 and 3, respectively)

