Follow up surveys will be conducted with study participants at 3 months. Please note that at this stage of the data collection, there will be three possible study participants groups for which we will provide individualized surveys, (1) those who were mapped during the social network mapping exercise and identified as a part of the network where the central promoter was randomized to control or intervention, (2) those who were not mapped or named during the baseline social network mapping exercise but received an HIVST with an incentive voucher (intervention) or referral voucher (control) from a central promoter, and (3) central promoters themselves. These surveys will assess self-reported HIV testing among study participants, whether they sought confirmatory testing, whether they linked to ART or PrEP, interactions they had with study promoters, as well as assess health behaviors. We will have three versions of the follow up survey which are attached to this protocol.

8.7 BIOSPECIMEN COLLECTION AND CLINICAL DATA TO ASSESS CONFIRMATORY TESTING, LINKAGE TO ART AND PREP, AND LONG TERM OUTCOMES

*Up to n=1500 participants**

* We do not know aprior the rate of care or prevention uptake so the total numbers are tentative.

Visit 2 (for 6 months) for new participants (those not mapped in the baseline but received self-tests with incentive vouchers (intervention) or referral vouchers (control) from promoters and then linked to care or prevention

Visit 4 (for 6 months) for baseline mapped and surveyed participants who received self-tests with incentive vouchers (intervention) or referral vouchers (control) from promoters and then linked to care or prevention

Visit 5 (for 6 months) for promoters who will have participated in the social network survey, baseline survey, and promoter trainings (visits 1 2 and 3, respectively) and then linked to care or prevention

We will obtain informed consent in clinics, from all of the study participants who opt to visit a study clinic for confirmatory testing, for the release of medical record data. The clinical data abstraction and follow

up bio-specimen collection will take place for two cohorts (1) those who HIV test, link to care and are enrolled in care and taking ARVs, and (2) those who HIV test, are HIV-negative, screened and eligible for and start PrEP. The chart abstraction data focused on 6-month outcomes will be collected retrospectively through the end of year 4, June 2023.

HIV-positive study participants

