9.3 STUDY INTERVENTION/EXPERIMENTAL MANIPULATION ADHERENCE

Because promoters (study participants and members of social networks) are primarily implementing the intervention, adherence will be encouraged by training at the outset, and periodic monitoring to ensure that the correct messages on HIVST, ARV and PrEP are being disseminated as needed.

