1.3.2 ANALYSIS OF THE PRIMARY ENDPOINT(S)

Primary Outcome: The primary outcome will be self-reported HIV testing in the past 3 months by participants, as measured in the 3-month follow-up surveys.

Primary Predictor: Cluster (social network) Randomized Arm (intent-to-treat), Intervention or Control.

Analytic Plan: For the test of the intervention effect on the primary outcome of self-reported HIV testing in past 3 months, we will utilize a cluster adjusted Pearson's Chi-square test comparing the proportion of subjects' HIV testing in the intervention versus the control arm. In secondary analysis, we will utilize multilevel mixed-effects logistic regression with cluster-adjusted standard errors and a binary outcome of reported HIV testing or not (including cluster as one of the levels with random effects allowed). We will

investigate factors that influence the probability of success of HIV testing, including characteristics of clusters (the close social networks' size and composition, metrics of connectedness, mean cluster self-testing rate), characteristics of the cluster's promoter (age, marital, HIV, ART, PrEP status, measures of the promoter's ties to close-social-network cluster members), and individual level characteristics (demographics, SES, prior HIV testing, duration in boat crew, self-reported HIV risk).

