### 8) Objectives:

This study aims to identify strategies needed to close gaps in the HIV care and prevention cascades in high priority populations and settings in sub-Saharan Africa. These gaps are most pronounced in men, who are less likely than women to test for HIV and seek HIV treatment or prevention services, and in high HIV incidence settings such as western Kenya. We will harness the power of peer influence within men's close social networks and leverage new technologies such as HIV self-tests and point-of-care PrEP adherence assays to increase

men's HIV testing rates and strengthen men's ongoing engagement in HIV care and prevention. We will pursue three aims:

- a. Aim 1: Determine whether providing HIV self-tests to network-central men for distribution to other men in their close social networks increases men's HIV testing uptake. We will conduct social network mapping in study communities in Siaya Country, Kenya to identify distinct close social networks of men. We will then randomize these social networks to intervention and control groups. Network-central, highly- connected men in each network will be recruited as "promoters", and receive HIVST training. Promoters in networks assigned to the intervention will then receive self-tests for distribution to men in their networks. Promoters in networks assigned to the control will instead distribute vouchers for free self-tests at nearby health clinics.
- b. Aim 2: Determine whether network-central promoters and small incentives can improve ART and PrEP uptake among men. We will test whether network-central promoters can enhance linkage to ART and PrEP after self-testing, thereby addressing a key limitation of HIVST. Promoters in the Aim 1 intervention group will be asked to distribute information and transport vouchers for ART or PrEP to men in their networks. Our primary hypothesis is that the intervention will result in higher rates of linkage to ART or PrEP (confirmatory testing and ART referral for positives, and PrEP screening for negatives).

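### The Aim 1 analysis set does not say whether promoters count, and no planned analysis shows testing among the other network members on their own

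*Protocol*

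**What the plan says.** **Outcome and set.** Protocol 1.3.2 defines the outcome: "The primary outcome will be self-reported HIV testing in the past 3 months by participants, as measured in the 3-month follow-up surveys". SAP 20) defines intent to treat as everyone randomised, whether or not his promoter gave him a kit. Neither text names promoters as counted or not counted.

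**Signs that promoters are in.**
- Protocol 8.6 makes them the third surveyed group: "and (3) central promoters themselves. These surveys will assess self-reported HIV testing among study participants".
- Protocol 8.5 draws them from the cohort: "Visit 3 for up to n=140 promoters from the study population of up to n=1000 men".
- Protocol 9.3: "Because promoters (study participants and members of social networks) are primarily implementing the intervention".
- SAP 19) covers the designated promoter in its definition of randomised exposure.

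**Signs that leave it open.** The SAP 20) remark about receiving a kit from one's promoter fits only the other members. Protocol 6.6 and 8.4 list network members and promoters side by side, as if they were two groups.

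**Objective.** The protocol synopsis asks whether "providing training and HIVST to select fishermen to distribute to other men in their close social networks increases" testing uptake in men. SAP 8) asks whether "providing HIV self-tests to network-central men for distribution to other men in their close social networks increases" the same thing. The hypothesis in the synopsis and in SAP 9) concerns men in intervention networks as a whole.

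**What promoters receive.** In the text on intervention promoters, Protocol 8.5 says "each network-central promoter will receive a test kit for himself". For control promoters, "a basic training will be provided to present the study, importance and benefit of HIV testing, care, and prevention", plus a voucher with information on where to test.

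**Separate analyses.** SAP 27) marks both sensitivity and subgroup analyses as not applicable, and SAP 29) requires no additional analyses.

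**The concern.** In each network one man is treated differently from the rest. He is trained, asked to promote testing and, in the intervention arm, handed a kit. If he is in the numerator and denominator, the arm difference mixes two things: the effect of being made a promoter, and the effect of a promoter on his peers. The second is what would justify secondary distribution as a strategy. As the plan stands, two analysts could build different primary datasets, and neither would have a prespecified result for the men the promoter is meant to reach. The existing secondary analyses do not fill the gap. The regressions use traits of the cluster's promoter as covariates, but do not list being a promoter as an individual covariate. The Aim 1 per-protocol set is intervention men who received a kit, which does not single promoters out either.

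**Working it through.** **Inputs from the documents.** Control 38%, intervention 52%, ICC 0.15, 70 clusters of 7 per arm (Protocol 1.2); two-sided 5% (SAP 16)); one promoter per network (Protocol 8.3). Promoter testing rates are not given and are assumed below. The size of 7 is taken to include the promoter.

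**Step 1. The plan's own figure.** Design effect = 1 + (7 − 1) × 0.15 = 1.90. Effective n per arm = 70 × 7 / 1.90 = 257.9. The two-proportion formula gives 89.4% power for 38% against 52%, so the stated 80% or greater holds.

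**Step 2. Share of promoters.** One in 7 is 14.3% (70 of 490 per arm). Protocol 8.5 gives 140 of 1,000, or 14%. At the SAP's size of 8 it is 12.5%.

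**Step 3. Range for promoter rates.** HIV prevalence is 24–26% in Protocol 4.1 and up to 32.1% among fisherfolk in SAP 10). Treatment uptake is 53–61% (Protocol 4.1). The share of men on ART is then 0.24 × 0.53 = 12.7% to 0.321 × 0.61 = 19.6%. If those men do not retest (an assumption), promoter testing cannot go much above 80–87%. The cases below stay within that limit.

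**Step 4. Gap and promoter share.** With d the intervention-minus-control difference:
- network gap = [(m − 1) × d_other + d_promoter] / m
- promoter share = d_promoter / [(m − 1) × d_other + d_promoter]

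**Step 5. Rejection rates.** These come from simulation at 70 × 7: beta-binomial other men with ICC 0.15, one independent promoter per cluster, a two-sided cluster-level t-test and 40,000 trials per case.

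| Promoters (int. vs control) | Other men | Network gap | Promoter share | Rejects, whole network | Rejects, other men only |
|---|---|---|---|---|---|
| 80% vs 70% | 38% vs 38% | 1.4 points | all | about 6.5% | 5% |
| 80% vs 60% | 38% vs 38% | 2.9 points | all | 11% | 5% |
| 85% vs 60% | 38% vs 38% | 3.6 points | all | 15% | 5% |
| 85% vs 60% | 42% vs 38% | 7.0 points | 51% | about 41% | about 14% |
| 85% vs 60% | 48% vs 38% | 12.1 points | 29% | 86% | 60% |

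Fourth row: (6 × 0.04 + 0.25) / 7 = 0.49 / 7 = 7.0 points, and 0.25 / 0.49 = 51%. Fifth row: (6 × 0.10 + 0.25) / 7 = 0.85 / 7 = 12.1 points, and 0.25 / 0.85 = 29%. With promoters at 60% in both arms and no effect in other men, the test rejects about 5% of the time, as it should.

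**Step 6. The opposite direction.** If promoters test equally in both arms (60–100%) and other men are at 52% against 38%, including promoters dilutes the gap from 14 to 6 × 14 / 7 = 12 points. Power is then 83–87%, against 87% for other men alone.

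**Step 7. Power without promoters.** 70 × 6: design effect 1.75, effective n = 420 / 1.75 = 240, power 87.2%.

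**The case against.** The best defence is that the whole-network comparison is what the trial set out to test. The objective sentence ends on testing uptake in men generally. Other men are named there as those who receive the kits, not as the only men whose testing counts. The hypothesis is about men in networks, and Protocol 6.5 assigns the arm condition to every member. That stands. A reader might infer that Aim 1 concerns only other men, or that including promoters inflates the type I error. The documents support neither. The rejection rates above are power for a true effect of assignment on whole networks, not false positives.

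The contrast between promoters may also be small, and the documents disagree about it. Protocol 8.5 describes a basic training for control promoters. The Aim 2 row of Protocol Table 2 gives them the same training and information, and SAP 8) has promoters in every network trained on self-testing. Control vouchers can be exchanged for free tests or self-tests (protocol synopsis, Known Potential Risks, SAP 8)), so a control promoter also has an easy route to a test. This is why large gaps, such as every intervention promoter testing, are not relied on here.

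Finally, promoters have their own survey version, so they could be split out after the fact. That is true, but a split chosen after the result is known carries less weight than one named beforehand.

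**Conclusion.** The point holds as a gap in specification and attribution, not as a flaw in the randomisation or the test. The documents do not say whether promoters are in the Aim 1 set. The default reading includes them at about 1 in 7, and no planned analysis separates them. With no effect in other men and assumed promoter rates from 80% vs 70% to 85% vs 60%, the whole-network test rejects about 6.5–15% of the time. With a small effect in other men (42% vs 38%) and promoters at 85% vs 60%, about half of a 7-point gap comes from promoters. All of these sizes rest on assumed promoter rates, and equal promoter rates would dilute the result instead. It should be fixed because a positive result could not otherwise be attributed to other men. Confidence is medium, since the true promoter contrast is unknown.

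**What to change.** 1. State in the protocol and SAP that the Aim 1 intent-to-treat set is all mapped, randomised network members, and say whether promoters are in it.
2. Prespecify, as a named key secondary or sensitivity analysis, the same cluster-adjusted comparison in members other than the promoter. Report promoter testing separately by arm.
3. Define the man left out as the designated promoter who consented before randomisation, by the same rule in both arms. A rule based on the top-ranked man alone would drop a refuser and keep the alternate who holds the kit.
4. Reconcile the order of events. Protocol 6.4 and SAP 10) require a consenting promoter before randomisation. Protocol 8.3 randomises first and then identifies promoters, with alternates for refusers, and Protocol 4.1.2 takes consent on arm-specific forms. If any alternate took over after allocation, repeat the analysis leaving out both the designated man and the man who served.

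**Cost.** A few sentences. No new data are needed, because the network data already identify the central man and promoters have their own survey version. Power of the non-promoter analysis is 87.2% against 89.4% at 70 × 7. Leaving out two men in every cluster would give 84.0% (70 × 5, design effect 1.60, effective n 218.75). Whether the non-promoter analysis should be the primary one is the sponsor's choice.

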8.8 QUALITATIVE STUDIES

Up to n=76 participants (for IDIs &FGDS) and n=30 promoters (KIIs)

Visit 4 for new participants (those not mapped in the baseline but received self-tests)

Visit 6 for baseline mapped and surveyed participants who received self-tests

Visit 7 for promoters

The qualitative data collection approach will include in-depth interviews with participants in intervention and control, key informant interviews with network-central promoters, and focus group discussions with study participants stratified by HIV status and study group. Within the sample of up to n=1000 men, a subsample of men will be sampled and recruited for participation in:

- 1. **In-depth interviews**. A sample of up to 40 participants, selected to be equally balanced across study arms (i.e. 20 men per arm);
- 2. **Key informant interviews**. A sample up to 15 promoters from the intervention, and 15 in the control arm.
- 3. **FGD groups**. 1-2 focus groups per study arm, with 8-12 participants in each group. FGDs will include participants from all study sites, stratified by HIV status.

Data will be collected at baseline and up to three follow-up periods corresponding to the timing of quantitative outcome measurements in Aims 1 through 3. The team will use a qualitative sampling strategy drawing from grounded theory (ref. K. Charmaz), in which sampling, data collection and analysis processes are iterative: baseline data will be used to define initial sampling categories (balance across study arms, sites and HIV status) for selection of the first several participants in each category. Thereafter the team will select additional participants according to new categories based upon emergent findings: sampling is completed when data are 'saturated', i.e. no emergent findings elicit a need for additional participants. Thresholds are defined for practical reasons of study schedule and budget. Recruitment will be iterative, using sample lists generated using data collected from the baseline BMU census and survey, among participants who indicate during the baseline informed consent process that they are will to be contacted for potential participation in qualitative research.

